## **Study Design**

The design of this research is a multi-centre, prospective open-label (single arm) trial using LYO- FMT (treatment) to prevent recurrence of CDI in patients with history of recurrent CDI or to control diarrhea in patients with refractory CDI.

The study participants, individuals over the age of 11 years able to consent and comply with treatment. Participants required to have laboratory or pathology-confirmed diagnosis of recurrent CDI based on the Society for Healthcare Epidemiology of America (SHEA) definition, where recurrence is defined as return of diarrhea and positive stool test after a period of symptom resolution within 8 weeks of the first episode and has received at least a 10-day course of oral vancomycin.

Thirty grams of fresh stool collected within 5 hours from a healthy screened donor to be placed in a 60mL sterile container. Stool be frozen at -80°C and undergo lyophilization. Lyophilized products to be stored at 2 to 8°C for up to 112 weeks inside a box to avoid light exposure. Reconstitute LYO-FMT using 30mL normal saline. The participants received 30mL of the reconstituted lyophilized product as a retention enema using a syringe with a catheter tip. Discontinue the antibiotic 24 - 48 hours prior to the scheduled FMT. Participants to receive LYO-FMT via retention enema(s) on day 1 and the second LYO-FMT between day 5 and day 8 following the first LYO-FMT.

## Participant eligibility criteria

### Participant inclusion criteria

- Age  $\geq$  12 years or older.
- Able to provide informed consent.
- Willing and able to comply with all the required study procedures.
- A positive stool test for *C. difficile* toxin/gene using either PCR or enzyme immunoassay within 3 months of recruitment unless patient taking treatment specifically for CDI for more than 3 months.
- History of at least  $\geq$  2 recurrent CDI where recurrence is defined as return of diarrhea consistent with CDI within 8 weeks following CDI symptom resolution for at least 24 hours after a minimum of 10-day course of standard antibiotic therapy for each episode and/or ongoing symptoms consistent with CDI\* (defined below) despite at least 7 days of treatment using oral vancomycin at a minimum dose of 250 mg four times daily.

\*Symptoms of CDI include: diarrhea defined as: 3 or more unformed bowel movements in 24 hours for a minimum of 2 days with no other causes for diarrhea

### Participant exclusion criteria

- Planned or actively taking another investigational product
- CDI symptom-free for 3 or more weeks following completion of CDI treatment
- Patients with neutropenia with absolute neutrophil count  $<0.5 \times 10^9/L$
- Evidence of toxic megacolon or gastrointestinal perforation on abdominal x-ray
- Active gastroenteritis due to *Salmonella*, *Shigella*, shiga-toxin producing *E. coli*, *Yersinia* or *Campylobacter*.
- Presence of colostomy
- Unable to tolerate FMT or enema for any reason.
- Requiring systemic antibiotic therapy for more than 7 days.
- Actively taking *Saccharomyces boulardii* or other probiotic; yogurt is allowed
- Severe underlying disease such that the patient is not expected to survive for at least 30 days.

### The duration of treatment and study period

Participants received LYO-FMT via retention enema(s) on day 1 and repeat on day 5 through day 8 following the first LYO-FMT.

Assess the participants at day 1 and with medical history (including concurrent medications and recent antibiotic use), clinical assessment. Reassessment, blood work, and a repeat LYO-FMT on day 5 (+3: between day 5 and 8 from the first). At study visits, assess for clinical response, treatment failure and adverse reactions by clinical assessment and laboratory test. Follow the participants at day-10, week 5 and week-13 and yearly for 2 years subsequent to the completion of treatment for any evidence of relapse, adverse event and overall health. With ongoing or recurrence of diarrhea, the participant(s) undergo medical history, physical examination, complete blood count, chemistry panel and stool for *C. difficile* toxin by EIA or PCR for *tcdB* gene. For treatment failures or relapse during the study period, participants receive repeat lyophilized or frozen FMT(s), based on the investigator's decision and availability of type of FMT or standard antibiotic therapy.

### **Sample size and the justification for the assumptions**

158 participants based on the sample size and efficacy result of the trial comparing frozen versus fresh FMT. The control (frozen) FMT efficacy was 85% and the lowest acceptable response rate for LYO-FMT is set at 70%. Based on a one-sided hypothesis test, the sample size is 152, accounting for 10% attrition with 5% significance and 85% power.

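### The sample-size section gives two unreconciled sizes, 158 and 152, and does not say which is the enrolment target

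*Combined protocol and SAP*

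**What the plan says.** Both figures stand in one short paragraph of the combined protocol and SAP, under Sample size and the justification for the assumptions.

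- The first sentence gives "158 participants based on the sample size and efficacy result of the trial comparing frozen versus fresh FMT".
- The second sets the planning rates: 85% for frozen FMT and 70% as the lowest acceptable rate for LYO-FMT.
- The third reads "Based on a one-sided hypothesis test, the sample size is 152, accounting for 10% attrition with 5% significance and 85% power".

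The 10% attrition is attached only to 152, as already included. The figure 158 is attributed to the earlier frozen-versus-fresh trial. No sentence connects the two or says which is the number to enrol. The Study Design section describes a single-arm, open-label, multi-centre trial and gives no size. The section Type of statistical analyses names no test, interval or responder cut-off.

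**The concern.** A sample-size section should leave the reader with one number to enrol and one number expected to be analysed. Here a reader finds two candidates for the first and none for the second. A site, an ethics board or a later reader of the results could take either 158 or 152 as the plan and find support in the text.

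At stake is whether the enrolment that was carried out can be checked against the plan. In a single-arm comparison with a fixed rate of 70%, the responder count needed for success depends on the number analysed, so an unsettled size also leaves that count unsettled. How much this matters in practice is a question of arithmetic.

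**Working it through.** **Inputs.** All come from the sample-size section: sizes 158 and 152; attrition 10%, included in 152; null rate 70%; expected rate 85%; one-sided 5% significance; 85% power. The single-arm design comes from Study Design. The plan names no test, so the exact binomial test is an assumption made here.

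**Step 1. Can attrition explain the gap?** The text says that 152 already allows for attrition, so a further inflation should not apply. The sums agree that none was made:

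- 152 / 0.9 = 168.9 and 152 × 1.1 = 167.2; neither is 158.
- 158 × 0.9 = 142.2 and 158 / 1.1 = 143.6; neither is 152.
- The gap is 158 − 152 = 6, and 6 / 158 = 3.8%.

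This rules out one explanation. It does not refute anything the plan asserts, because the plan never says that attrition leads from one figure to the other.

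**Step 2. What difference does the choice make?** For each n, take the smallest c with P(X ≥ c | n, 0.70) ≤ 0.05. Type I error is that probability; power is P(X ≥ c | n, 0.85). The evaluable numbers after 10% loss are 152 × 0.9 = 136.8, taken as 137, and 158 × 0.9 = 142.2, taken as 142.

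| Number analysed | Cut-off | As a rate | Type I error | Power at 85% |
|---|---|---|---|---|
| 152 | 117 | 77.0% | 3.45% | 99.7% |
| 158 | 121 | 76.6% | 4.05% | 99.8% |
| 137 | 106 | 77.4% | 3.42% | 99.4% |
| 142 | 109 | 76.8% | 4.53% | 99.7% |

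**Step 3. What if the favourable size were chosen?** Summing exactly over the first 152 participants and the next 6, the probability at a true 70% that at least one of the two tests passes is 4.42%. For 137 and the next 5 it is 4.77%. Both are below 5%. The verdicts at 152 and 158 differ in 1.3% of trials at a true 70%, 6.4% at 75%, 7.1% at 77%, 4.1% at 80% and 0.16% at 85%.

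**Step 4. Does either figure follow from the stated inputs?** For one proportion, the score-type formula is

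n = [(z₀.₉₅ √(p₀(1 − p₀)) + z₀.₈₅ √(p₁(1 − p₁))) / (p₁ − p₀)]²

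With p₀ = 0.70, p₁ = 0.85, z₀.₉₅ = 1.645 and z₀.₈₅ = 1.036:

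n = [(1.645 × 0.4583 + 1.036 × 0.3571) / 0.15]² = 56.1, so 57 evaluable.

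Enrolment after attrition is 57 / 0.9 = 63.3, so 64. The exact binomial test first reaches 85% power at 57 and stays at or above it from 65, which gives 65 / 0.9 = 72.2, so 73 enrolled. Other one-sided normal variants run from 46 to 76 enrolled. Neither 152 nor 158 is reproduced, so the inputs cannot show which of the two was meant.

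**The case against.** The strongest reply is that the two figures need not conflict. The paragraph can be read as a target of 158 with 152 as the calculated minimum, and enrolling 6 more than the calculation requires is no error. Alternatively, 158 may describe the earlier trial. Either reading is possible. The text states neither, and they differ on the point that matters: under the first, 158 is the number to enrol; under the second, it is background. The reply reduces the fault to a missing explanation but does not remove it.

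Three stronger readings are tempting, and the documents do not support them.

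- A reader might infer that the two sizes are why the trial has no pass mark. The plan names no test, interval or responder cut-off anywhere, so the pass mark would be missing even with one size. The cut-offs above rest on an assumed test.
- A reader might infer that two printed targets in an open-label trial create a material risk of stopping at whichever one passes. Nothing in the text suggests that intention, and the error would still be 4.42%, or 4.77% after attrition. Against a fixed 158 (4.05%) or 142 (4.53%), the rise is about 0.4 or 0.2 percentage points.
- A reader might call this a failed attrition sum. The plan claims no such link between the figures.

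It can also be said that the unsupported size is the larger problem. That is fair, but the two are separate: correcting the calculation would not remove the second figure, and deleting one figure would not justify the other.

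**Conclusion.** The point holds as an unreconciled statement of a core design figure. The same trial is given two sizes, 158 and 152, with no indication of which is the enrolment target, and the attrition allowance cannot account for the difference.

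The statistical consequence is small. The cut-off is about 77% at either size, power exceeds 99% at a true 85% even after 10% loss, and error remains under 5% in the worst use of the ambiguity. The verdicts would differ in 6 to 7% of trials only if the true rate were near 75 to 77%, well below the planning rate. These results assume an exact one-sided binomial test against 70% at the 5% level and, where stated, exactly 10% loss. The contradiction itself rests on no assumption beyond the text.

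The case for a correction is that the plan should state its own size once, not that the trial's conclusion is in danger.

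**What to change.** In the sample-size section:

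1. State one enrolment target and say that it includes the 10% attrition.
2. Give the matching evaluable number: about 137 if the target is 152, or 142 if it is 158.
3. Delete the other figure, or label what it is, for example the calculated minimum or the size of the earlier trial.
4. State that enrolment ends at the target whatever the running result.

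At the same time, check the chosen figure against the stated inputs, which call for only about 57 to 65 evaluable participants (64 to 73 enrolled). Either give the formula and assumptions that lead to the larger number, or say that it was chosen for another reason.

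The cost is a sentence or two in one section, with no extra participants.

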This study is designed to be open-labeled to evaluate the efficacy of LYO-FMT (versus historical controls) as expeditiously as possible and to minimize the time and cost associated with conducting a two-armed randomized controlled trial given that the efficacy of frozen or fresh FMT is known to be 85%. The result of this trial will be useful to inform policy makers and to assist in formulating practice guidelines. The decision to pursue this open-labeled trial is based on the recent initiatives to optimize the utilization of limited resources available for conducting clinical trials. The US Food and Drug Administration and the United Kingdom's National Institute for Health Research Health Technology Assessment Programme launched guidance on adaptive research designs to increase the speed and the efficiency of clinical trials. An open-label clinical trial to add an arm to existing study is an example of such study, which can lead to rapid results with less cost. This in turn will lead to providing the "best" therapies to as many patients as possible.

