## **Study hypothesis**

- Administration of 2 enemas of LYO-FMT will have similar efficacy as control (frozen-historical) FMT in reducing the rates of recurrence of CDI.

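### The sample size of 152 does not follow from its printed inputs: against a fixed 70% benchmark they need about 64 to 73 enrolled, and 152 gives about 99% power rather than 85%

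*Combined protocol and SAP*

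**What the plan says.** All the inputs are in the combined protocol and SAP, under the heading Sample size and the justification for the assumptions. That section opens with the target: "158 participants based on the sample size and efficacy result of the trial comparing frozen versus fresh FMT". It then gives the two rates: "The control (frozen) FMT efficacy was 85% and the lowest acceptable response rate for LYO-FMT is set at 70" per cent. It ends with the calculation: "Based on a one-sided hypothesis test, the sample size is 152, accounting for 10% attrition with 5% significance and 85% power".

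The Study Design section describes a "prospective open-label (single arm) trial". The comparator is described in two ways. The introduction says that "the efficacy of frozen or fresh FMT is known to be 85" per cent, which treats 85% as a fixed quantity. The same section says the aim is to "evaluate the efficacy of LYO-FMT (versus historical controls) as expeditiously as possible", and remarks: "An open-label clinical trial to add an arm to existing study is an example of such study". The Study hypothesis section says that LYO-FMT "will have similar efficacy as control (frozen-historical) FMT in reducing the rates of recurrence of CDI".

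The section on type of statistical analyses refers only to standard methods for a binary outcome. No section says whether 70% is a fixed null value or a margin against a control sample, gives a control-group size, or names a test.

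**The concern.** In a single-arm trial, a lowest acceptable rate of 70% and an expected rate of 85% would normally be the null and alternative of a one-sample test. A 15-point difference at one-sided 5% and 85% power needs far fewer than 152 participants, so either the power or one of the other inputs does not belong to this N.

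The analysis section names no test, so the sample-size paragraph is the only place where a reader could learn what hypothesis the trial addresses. Showing that the response rate exceeds a fixed 70% is a different claim from showing that it is close to that of a frozen-FMT control sample, and the bar for success differs too. If N cannot be traced to its inputs, neither claim can be identified as the one planned.

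**Working it through.** **Inputs**, all from the sample-size section except the design, which is from Study Design: null 0.70, alternative 0.85, one-sided 5% (z = 1.645), power 85% (z = 1.036), attrition 10%, single arm, stated N = 152.

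**1. Attempt to reproduce 152: one sample, fixed 70%**

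- Normal formula with null and alternative variances: ((1.645 × √0.21 + 1.036 × √0.1275) / 0.15)² = 56.1, so 57 evaluable; 57/0.9 = 63.3, so 64 enrolled.
- Continuity-corrected: 63 evaluable; 63/0.9 = 70 enrolled.
- Exact binomial: power first reaches 85% at n = 57 (46 or more responders, size 0.049, power 0.862). It stays at or above 85% from n = 65 (52 or more, size 0.048, power 0.900); 65/0.9 = 72.2, so 73 enrolled.
- Null variance only, the most conservative choice: (1.645 + 1.036)² × 0.21 / 0.15² = 67.1, so 68 evaluable; 68/0.9 = 75.6, so 76 enrolled.

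The stated 152 is 2.0 to 2.4 times these figures (152/76 = 2.0; 152/64 = 2.4). Even a two-sided 5% one-sample test needs at most 94 enrolled across the variance choices tried.

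**2. Power that the stated N gives against a fixed 70%** (exact one-sided 5% binomial)

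| Enrolled | Evaluable | Responders needed | Size | Power at a true 85% |
|---|---|---|---|---|
| 152 | 136 | 105 | 0.038 | 99.4% |
| 152 | 137 | 106 | 0.034 | 99.4% |
| 158 | 142 | 109 | 0.045 | 99.7% |

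Evaluable numbers come from 152 × 0.9 = 136.8 and 158 × 0.9 = 142.2. Exact power equals 85% at a true rate of about 80.5% with 137 evaluable and about 79.9% with 142.

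**3. Routes that do reach 152** (inferred; the documents state neither)

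- One-sample, one-sided 5%, 70% against 80%: ((1.645 × √0.21 + 1.036 × √0.16) / 0.10)² = 136.5; 136.5/0.9 = 151.7, so 152. This keeps everything printed except the 85% rate.
- Two equal groups, 70% against 85%, two-sided 5%, pooled null variance: (1.960 × √(2 × 0.775 × 0.225) + 1.036 × √(0.1275 + 0.21))² / 0.15² = 137.6 per group; 137.6 × 1.1 = 151.4, so 152. This contradicts the one-sided test and assumes a control group of equal size. Dividing by 0.9 instead gives 138/0.9 = 153.3, so 154.

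At the printed one-sided 5%, two equal groups give 111 per group (124 after attrition) with pooled variance, 108 (120) unpooled, 124 (138) continuity-corrected, and 82 (92) for a 15-point non-inferiority margin. None gives 152.

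**4. One-sided comparison with a finite historical control group**

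The control size m is an assumption here, because none is printed. Normal-approximation power with 137 evaluable:

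| Comparison | m = 58 | m = 80 | m = 100 |
|---|---|---|---|
| 15-point margin, 85% in both groups | 85.0% | 91.0% | 93.9% |
| 70% vs 85%, unpooled variance | 79.1% | 85.0% | 88.2% |
| 70% vs 85%, pooled null variance | 73.1% | 81.7% | 86.3% |

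So 152 can be matched with about 58, 80 or 93 to 94 controls, depending on the test. These sizes come from solving backwards and have no basis in the documents.

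**The case against.** The strongest reply is that this was never a test against a fixed 70%. The introduction speaks of historical controls and of adding an arm to an existing study, the hypothesis names a frozen historical control, and the sample-size section ties the target to the earlier frozen-versus-fresh trial. On that view the 99% figure answers a question the sponsor did not ask, and the control size may be known from that earlier trial.

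Part of this stands. No section says that 70% is a fixed null, so the 99% figure is conditional on that reading, and an unprinted control size may still be known to the sponsor. But the historical reading does not rescue the paragraph: at the printed one-sided 5%, N turns on the missing control size and on a choice of test. Nor is the fixed-benchmark reading the weaker one. Changing only the expected rate, from 85% to 80%, reproduces 152.

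Some stronger readings are tempting and are not supported:

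- A reader might infer that the trial is underpowered. On the fixed reading it has more power than stated; on the historical reading the documents show no loss of power, only dependence on an unknown.
- A reader might infer that the sponsor used 80%, or a two-sided two-group formula. Both fit, so neither is established.
- A reader might take 158 and 152 as a contradiction. The larger may simply be the adopted target and the smaller the calculated minimum.
- A reader might infer that enrolment should be cut. Nothing here calls for that.

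**Conclusion.** The point holds as a failure to reproduce a stated N and power, and should be fixed. No reading that uses only the printed inputs gives 152. The one-sample result is robust to the choice of formula, because even the most conservative one-sided version gives half the stated number.

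The 99.4% power rests on three assumptions: 70% is a fixed null, the test is an exact one-sided 5% binomial, and the 10% who drop out leave the denominator. Under the first of these, the printed 85% power probably belongs to a true rate of about 80%; that is an inference. Confidence is high that 152 does not follow from what is printed, and lower as to how it arose. The consequence is for interpretation, since the hypothesis behind the number cannot be recovered.

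**What to change.** Restate the sample-size paragraph so that N, test, rates and power agree.

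- **If 70% is a fixed benchmark:** name the test, and either print power of about 99% at a true rate of 85%, or say that the 85% power applies at a true rate of about 80%.
- **If a historical comparison was used:** print the control-group size, the test, its sidedness and any margin.
- **In either case:** say whether dropouts leave the denominator. Any success bar depends on this. By an exact one-sided 5% binomial test against 70%, which is an assumption because the plan names no test, the bar would be 109 of 142 evaluable, or 121 of 158 if everyone enrolled counts. These are illustrations, not rules found in the plan.
- **For clarity:** say that 158 is the adopted target and 152 the calculated minimum, if that is so.

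The cost is a rewritten paragraph, with no added participants and no change to enrolment. It is slightly more than an edit, because the sponsor has to confirm the null hypothesis, the test and the analysis set.

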### **Type of statistical analyses**

The clinical response rate is to be determined using standard binary outcome protocols.

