## **Study outcomes**

### **Primary endpoint**

- Evaluate treatment efficacy as determined by no recurrence of CDI-related diarrhea at 13 weeks after receiving up to 2 LYO-FMTs without the need for an intervention (antibiotics or frozen or LYO-FMT as per investigator's decision) specifically for recurrence of CDI.

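### Does the unstated denominator for the primary response rate, and for the historical 85% behind it, call for a change to the plan?

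*Combined protocol and SAP*

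**What the plan says.** The section on type of statistical analyses consists of "The clinical response rate is to be determined using standard binary outcome protocols". No analysis population or missing-outcome rule appears there or elsewhere.

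The primary endpoint is "no recurrence of CDI-related diarrhea at 13 weeks after receiving up to 2 LYO-FMTs without the need for an intervention" for CDI recurrence. A documented recurrence or CDI re-treatment before week 13 is therefore already a non-success. The endpoint does not cover a participant who is lost event-free or who dies of something else before week 13. The exclusion criteria look only 30 days ahead ("Severe underlying disease such that the patient is not expected to survive for at least 30 days"), so some other-cause deaths before week 13 are possible. The first secondary endpoint counts a death as treatment failure only when CDI was its direct cause, but that does not settle the primary endpoint.

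On the benchmark, the introduction justifies the single-arm design "given that the efficacy of frozen or fresh FMT is known to be 85" per cent. The hypothesis is that LYO-FMT "will have similar efficacy as control (frozen-historical) FMT in reducing the rates of recurrence of CDI". The sample-size section states: "The control (frozen) FMT efficacy was 85% and the lowest acceptable response rate for LYO-FMT is set at 70" per cent, and "the sample size is 152, accounting for 10% attrition". None of these places gives the analysis set, the loss rule or the loss share behind the 85%.

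**The concern.** In a randomised trial one counting rule applies to both arms, so much of its effect cancels. Here a single-arm rate is set beside a fixed historical figure, and nothing ties the two rules together. If the 85% counted losses as failures and LYO-FMT left them out, LYO-FMT would be flattered. In the reverse case it would be penalised. No concurrent arm would reveal either. The trial is also open-label, so an unwritten rule could be settled after outcomes are known. At stake would be a false pass or a false fail against the 70% floor.

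**Working it through.** **Inputs.** From the sample-size section: historical rate 85%, floor 70%, one-sided 5% test, 85% power, 10% attrition, and participant numbers of 158 and 152.

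**The plan's own figure.** A one-sample calculation gives n = [(1.645·√(0.70·0.30) + 1.036·√(0.85·0.15)) / 0.15]² = 56.1, so 57, or 57/0.90 = 63.3, so 64 with attrition. The stated 152 is not reproduced this way. That is a separate matter. It means only that the trial is far larger than this test needs.

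**Assumptions for the mismatch figures.** 158 are treated. The undetermined are all post-treatment and event-free: 16 (10%), 8 or 3 people, leaving n = 142, 150 or 155 observed. The floor is read as lying on the historical scale, and both studies are given the same loss share.

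**Critical counts** (fewest successes with exact binomial tail ≤ 5% at 70%): 121/158, 109/142, 115/150, 119/155.

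**Gap between 85% and the floor on the historical scale**
- 85% counts losses as failures, LYO-FMT leaves them out: 85 − 70·n/158.
- 85% leaves losses out, LYO-FMT counts them as failures: 85 − 70·158/n.

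**Pass probabilities**
- First mismatch, product at the floor: P(X ≥ critical count | n, 0.70·158/n).
- Second mismatch, product equal to control: P(X ≥ 121 | n, 0.85).

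| Undetermined | Gap, first mismatch | Floor product passes | Gap, second mismatch | Equal product passes |
|---|---|---|---|---|
| 16 | 22.1 points | 67% | 7.1 points | 53% |
| 8 | 18.5 points | 24% | 11.3 points | 94% |
| 3 | 16.3 points | 8% | 13.6 points | 99% |

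With 152 treated and 15 undetermined, the two pass rates are 58% and 51%. With matched rules and the same loss share in both studies, type I error runs from 1.9% to 4.5% and power exceeds 99%.

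**Does matching the rule cure it?** Drop the equal-loss assumption and let both studies count losses as failures, with 121/158 needed to pass. Let b be the benchmark's loss share, so success among those observed is 0.85/(1 − b) for an equal product and 0.70/(1 − b) at the floor.
- b = 0, 16 LYO-FMT losses: P(X ≥ 121 | 142, 0.85) = 53% for an equal product.
- b = 2%, 16 losses: success rate 0.867, pass rate 75%.
- b = 10%, 3 losses: a floor product has success rate 0.778 among 155 and passes 51% of the time.

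So a matched failure rule can do as much damage as a mismatch. Conversely, in the first mismatch with b = 0, a floor product passes P(X ≥ 109 | 142, 0.70) = 4.5% of the time, not 67%; with b = 2% it passes about 9%. The alarming figure rests on a benchmark loss share that the documents do not give.

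**The floor read literally.** Taken as an absolute 70% for LYO-FMT, it does not move with the benchmark's counting rule. Leaving out 16 undetermined, type I error is 4.5% and power at 85% is 99.7% (109/142).

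**The case for a change.** The strongest case for a change is that the silence is real and is not explained by redaction, and that a short statement would remove it. Even with the floor fixed at 70%, the choice of rule can decide the result. With 16 undetermined and 85% success among the 142 observed, the count falls between 109 and 120 with probability 47%. It then passes if losses are left out and fails if they are counted as failures, since 85% of 142 is only 76.4% of 158 and the critical fraction is 121/158 = 76.6%. An open-label trial gives room to choose.

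That stands as arithmetic, but it is confined to the upper end. The probability of disagreement falls to 6% with 8 undetermined and 0.5% with 3. The plan's 10% is general attrition, and nothing says that all of it falls after treatment and before any event. The room to choose is also narrow: the numbers treated, undetermined and successful are enough for any reader to recompute the rate under either rule.

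An instruction to adopt the benchmark's denominator would not be a safe improvement. If that trial counted losses as failures but lost few people, following it here with 16 losses would lower an equal product's chance of passing from 99.7% to 53%.

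**Conclusion.** The plan leaves out the primary analysis set, the handling of undetermined week-13 outcomes and the basis of the 85%. This is a gap in documentation, not a demonstrated error. No passage shows the two rates to be built differently, and either rule is defensible when the rules and loss shares are alike. The attrition allowance already suggests that lost participants leave the analysed number. The natural reading is therefore the observed week-13 outcomes of treated participants, with a losses-as-failures count beside them as routine reporting.

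The shift from 15 points to about 22 or 7 holds only if there is a mismatch, the floor sits on the historical scale, and both studies have about 10% undetermined. At about 2% the gap is 16.3 or 13.6 points. If 70% is an absolute floor, the gap does not shift at all. No change to the plan follows. In reading the result, the similarity to 85% should be taken as a historical comparison whose denominator and loss share the documents do not give.
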